### 8.3.5 ADVERSE EVENT REPORTING

The study period during which AEs must be reported is defined as from the initiation of any study treatment or randomization through the end of the study intervention follow-up.

Any AE (clinical sign, symptom, or disease) temporally associated with the use of this study device, whether or not considered related to the study device, shall be documented on the AE CRF, except those physical assessment findings that are considered to be clinically insignificant.

All AEs meeting the above noted criteria reported by the subject or observed by the Investigator will be individually listed. The description of the event (confirmed diagnosis, if available), date of onset, date of resolution, severity and relationship to study device, action taken, outcome, and seriousness will be reported.

---

### 8.3.6 SERIOUS ADVERSE EVENT REPORTING

For any **SAE** the Principal Investigator must notify the Sponsor's Medical Monitor, within 24 hours of becoming aware of the event and send the completed Serious Adverse Event/Unanticipated Adverse Device Effect (SAE/UADE) Report to the Sponsor's Medical Monitor within 48 hours. In addition, all IRB reporting requirements will be followed.

Any SAE or UADE must be reported to the Sponsor's Medical Monitor via telephone, fax, or email within 24 hours of becoming aware of the event:

#### 8.3.7 REPORTING EVENTS TO PARTICIPANTS

Not applicable.

---

#### 8.3.8 EVENTS OF SPECIAL INTEREST

Not applicable.

### 8.4 UNANTICIPATED PROBLEMS

---

#### 8.4.1 DEFINITION OF UNANTICIPATED PROBLEMS (UP)

The Office for Human Research Protections (OHRP) considers unanticipated problems involving risks to participants or others to include, in general, any incident, experience, or outcome that meets **all** of the following criteria:

- Unexpected in terms of nature, severity, or frequency given (a) the research procedures that are described in the protocol-related documents, such as the Institutional Review Board (IRB)-approved research protocol and informed consent document; and (b) the characteristics of the participant population being studied;
- Related or possibly related to participation in the research ("possibly related" means there is a reasonable possibility that the incident, experience, or outcome may have been caused by the procedures involved in the research); and
- Suggests that the research places participants or others at a greater risk of harm (including physical, psychological, economic, or social harm) than was previously known or recognized.

This definition could include an unanticipated adverse device effect, any serious adverse effect on health or safety or any life-threatening problem or death caused by, or associated with, a device, if that effect, problem, or death was not previously identified in nature, severity, or degree of incidence in the investigational plan or application (including a supplementary plan or application), or any other unanticipated serious problem associated with a device that relates to the rights, safety, or welfare of subjects (21 CFR 812.3(s)).

---

#### 8.4.2 UNANTICIPATED ADVERSE DEVICE EFFECT (UADE) REPORTING

The investigator will report unanticipated problems (UPs) to the reviewing Institutional Review Board (IRB) and to the Data Coordinating Center (DCC)/lead principal investigator (PI). The UP report will include the following information:

- Protocol identifying information: protocol title and number, PI's name, and the IRB project number;
- A detailed description of the event, incident, experience, or outcome;
- An explanation of the basis for determining that the event, incident, experience, or outcome represents an UP;
- A description of any changes to the protocol or other corrective actions that have been taken or are proposed in response to the UP.

An Unanticipated Adverse Device Effect is described as any serious adverse effect on health or safety or any life-threatening problem or death caused by or associated with a device, if that effect, problem, or death was not previously identified in nature, severity, or degree of incidence in the investigational plan or application (including a supplementary plan or application), or any other unanticipated serious problem associated with a device that relates to the rights, safety, or welfare of subjects (21 CFR 812.3(s)).

An investigator shall submit to the sponsor and to the reviewing Institutional Review Board (IRB) a report of any unanticipated adverse device effect occurring during an investigation as soon as possible, but in no event later than 10 working days after the investigator first learns of the effect (21 CFR 812.150(a)(1)).

A sponsor who conducts an evaluation of an unanticipated adverse device effect under 812.46(b) shall report the results of such evaluation to the Food and Drug Administration (FDA) and to all reviewing IRB's and participating investigators within 10 working days after the sponsor first receives notice of the effect. Thereafter the sponsor shall submit such additional reports concerning the effect as FDA requests (21 CFR 812.150(b)(1)).

## 9 STATISTICAL CONSIDERATIONS

### 9.1 STATISTICAL HYPOTHESES

- Primary Efficacy Endpoint(s):
  1. Dose response comparison for pain relief at 2 hours

- a. Null hypothesis:  
 $H_0: \pi_A - \pi_S = 0$ ; where  $\pi_A$  is the proportion of subjects who show pain relief at 2 hours after active treatment (flow rate of x or Y) and  $\pi_S$  is the equivalent value for the sham-control treatment group.
  - b. Alternative hypothesis:  
 $H_a: \pi_A - \pi_S > 0$ ; where  $\pi_A$  is the proportion of subjects who show pain relief at 2 hours after active treatment (flow rate of x or Y) and  $\pi_S$  is the equivalent value for the sham-control treatment group.
- Secondary Efficacy Endpoint(s):
    1. Dose response comparison for pain relief immediately and 24 hours post treatment.
      - a. Null hypotheses:
        - i.  $H_0: \pi_A - \pi_S = 0$ ; where  $\pi_A$  is the proportion of subjects who show pain relief immediately after active treatment (flow rate of x or Y) and  $\pi_S$  is the equivalent value for the sham-control treatment group.
        - ii.  $H_0: \pi_A - \pi_S = 0$ ; where  $\pi_A$  is the proportion of subjects who show pain relief at 24 hours after active treatment (flow rate of x or Y) and  $\pi_S$  is the equivalent value for the sham-control treatment group.
      - b. Alternative hypothesis:
        - iii.  $H_a: \pi_A - \pi_S > 0$ ; where  $\pi_A$  is the proportion of subjects who show pain relief immediately after active treatment (flow rate of x or Y) and  $\pi_S$  is the equivalent value for the sham-control treatment group.
        - iv.  $H_a: \pi_A - \pi_S > 0$ ; where  $\pi_A$  is the proportion of subjects who show pain relief at 24 hours after active treatment (flow rate of x or Y) and  $\pi_S$  is the equivalent value for the sham-control treatment group.
    2. Dose response comparison for pain freedom immediately, 2 hours, and 24 hours post treatment.
      - a. Null hypotheses:
        - i.  $H_0: \pi_A - \pi_S = 0$ ; where  $\pi_A$  is the proportion of subjects who show pain freedom immediately after active treatment (flow rate of x or Y) and  $\pi_S$  is the equivalent value for the sham-control treatment group
        - ii.  $H_0: \pi_A - \pi_S = 0$ ; where  $\pi_A$  is the proportion of subjects who show pain freedom 2 hours after active treatment (flow rate of x or Y) and  $\pi_S$  is the equivalent value for the sham-control treatment group.
        - iii.  $H_0: \pi_A - \pi_S = 0$ ; where  $\pi_A$  is the proportion of subjects who show pain freedom 24 hours after active treatment (flow rate of x or Y) and  $\pi_S$  is the equivalent value for the sham-control treatment group.
      - b. Alternative hypothesis:
        - i.  $H_a: \pi_A - \pi_S > 0$ ; where  $\pi_A$  is the proportion of subjects who show pain freedom immediately after active treatment (flow rate of x or Y) and  $\pi_S$  is the equivalent value for the sham-control treatment group.
        - ii.  $H_a: \pi_A - \pi_S > 0$ ; where  $\pi_A$  is the proportion of subjects who show pain freedom 2 hours after active treatment (flow rate of x or Y) and  $\pi_S$  is the equivalent value for the sham-control treatment group.
        - iii.  $H_a: \pi_A - \pi_S > 0$ ; where  $\pi_A$  is the proportion of subjects who show pain freedom 24 hours after active treatment (flow rate of x or Y) and  $\pi_S$  is the equivalent value for the sham-control treatment group.

3. Dose response comparison for relief of migraine associated symptoms (nausea/vomiting, photophobia, phonophobia) immediately, 2 hours, and 24 hours post treatment.
  - a. Null hypotheses:
    - i.  $H_0: \pi_A - \pi_S = 0$ ; where  $\pi_A$  is the proportion of subjects who show relief from migraine associated symptoms immediately after active treatment (flow rate of x or Y) and  $\pi_S$  is the equivalent value for the sham-control treatment group.
    - ii.  $H_0: \pi_A - \pi_S = 0$ ; where  $\pi_A$  is the proportion of subjects who show relief from migraine associated symptoms 2 hours after active treatment (flow rate of x or Y) and  $\pi_S$  is the equivalent value for the sham-control treatment group.
    - iii.  $H_0: \pi_A - \pi_S = 0$ ; where  $\pi_A$  is the proportion of subjects who show relief from migraine associated symptoms 24 hours after active treatment (flow rate of x or Y) and  $\pi_S$  is the equivalent value for the sham-control treatment group.
  - b. Alternative hypothesis:
    - i.  $H_a: \pi_A - \pi_S > 0$ ; where  $\pi_A$  is the proportion of subjects who show relief from migraine associated symptoms immediately after active treatment (flow rate of x or Y) and  $\pi_S$  is the equivalent value for the sham-control treatment group.
    - ii.  $H_a: \pi_A - \pi_S > 0$ ; where  $\pi_A$  is the proportion of subjects who show relief from migraine associated symptoms 2 hours after active treatment (flow rate of x or Y) and  $\pi_S$  is the equivalent value for the sham-control treatment group.
    - iii.  $H_a: \pi_A - \pi_S > 0$ ; where  $\pi_A$  is the proportion of subjects who show relief from migraine associated symptoms 24 hours after active treatment (flow rate of x or Y) and  $\pi_S$  is the equivalent value for the sham-control treatment group.
4. Dose response comparison for freedom from migraine associated symptoms (nausea/vomiting, photophobia, phonophobia) immediately, 2 hours, and 24 hours post treatment.
  - a. Null hypotheses:
    - i.  $H_0: \pi_A - \pi_S = 0$ ; where  $\pi_A$  is the proportion of subjects who show freedom from migraine associated symptoms immediately after active treatment (flow rate of x or Y) and  $\pi_S$  is the equivalent value for the sham-control treatment group.
    - ii.  $H_0: \pi_A - \pi_S = 0$ ; where  $\pi_A$  is the proportion of subjects who show freedom from migraine associated symptoms 2 hours after active treatment (flow rate of x or Y) and  $\pi_S$  is the equivalent value for the sham-control treatment group.
    - iii.  $H_0: \pi_A - \pi_S = 0$ ; where  $\pi_A$  is the proportion of subjects who show freedom from migraine associated symptoms 24 hours after active treatment (flow rate of x or Y) and  $\pi_S$  is the equivalent value for the sham-control treatment group.
  - b. Alternative hypothesis:
    - i.  $H_a: \pi_A - \pi_S > 0$ ; where  $\pi_A$  is the proportion of subjects who show freedom from migraine associated symptoms immediately after active treatment (flow rate of x or Y) and  $\pi_S$  is the equivalent value for the sham-control treatment group.
    - ii.  $H_a: \pi_A - \pi_S > 0$ ; where  $\pi_A$  is the proportion of subjects who show freedom from migraine associated symptoms 2 hours after active treatment (flow rate of x or Y) and  $\pi_S$  is the equivalent value for the sham-control treatment group.

- rate of  $x$  or  $Y$ ) and  $\pi_S$  is the equivalent value for the sham-control treatment group.
- iii.  $H_a: \pi_A - \pi_S > 0$ ; where  $\pi_A$  is the proportion of subjects who show freedom from migraine associated symptoms 24 hours after active treatment (flow rate of  $x$  or  $Y$ ) and  $\pi_S$  is the equivalent value for the sham-control treatment group.
5. Superiority comparison for use of rescue medication between 2 and 24 hours.
- a. Null hypothesis:  $H_0: \pi_S - \pi_A = 0$ ; where  $\pi_A$  is the proportion of subjects take rescue medication between 2 and 24 hours after active treatment (flow rate of  $x$  or  $Y$ ) and  $\pi_S$  is the equivalent value for the sham-control treatment group.
- b. Alternative hypothesis:  $H_a: \pi_S - \pi_A > 0$ ; where  $\pi_A$  is the proportion of subjects who take rescue medication between 2 and 24 hours after active treatment (flow rate of  $x$  or  $Y$ ) and  $\pi_S$  is the equivalent value for the sham-control treatment group.

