**Endpoints:**

Primary Endpoints:

- Safety of the CoolStat device measured by incidence of adverse events
- Tolerability of the CoolStat device by percent of subjects who fail to complete the full treatment session.
- Pain relief at 2 hours post treatment.

Secondary Endpoints:

- Pain relief immediately post treatment and at 24 hours post treatment.
- Pain freedom immediately, 2 hours, and 24 hours post treatment.
- Relief of migraine associated symptoms (nausea/vomiting, photophobia, phonophobia) immediately, 2 hours, and 24 hours post treatment.
- Freedom from migraine associated symptoms (nausea/vomiting, photophobia, phonophobia) immediately, 2 hours, and 24 hours post treatment.
- Use of rescue medication between 2 and 24 hours.
- % of subjects who believe they received active treatment in each arm.

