### 8.1.4 POST TREATMENT EVALUATION 2 (2 HOURS)

The subject will remain in the clinic for 2 hours after they complete treatment session and will be monitored for adverse events during that time period. During this 2 hour period, subjects will remain in the exam room or another quiet space in the clinic, and will be allowed to rest. Subjects will be asked to delay taking rescue medications until this 2 hour period is over, if possible.

At the end of the 2 hour monitoring period, subjects will repeat the migraine symptom questionnaire, and the investigator or his designee will obtain the subject's tympanic membrane temperature, blood pressure, and oxygen saturation and record the data in the Case Report Form.

The investigator or his designee will record any adverse events.

Upon completion of these items, the subject may resume other care activities.

The study team member will record use of any rescue medications during this 2-hour period.

---

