### 8.1.5 POST TREATMENT EVALUATION 3 (24 HOURS)

The investigator or his designee will call the subject approximately twenty-four hours after CoolStat treatment was completed and ask the subject to complete the migraine questionnaire over the phone. If the subject cannot be reached, study personnel will continue to try to reach the subject on regular intervals over the course of this day and the next consecutive 2 days. It will be noted in the case report forms if the subject could not be reached for the final follow up.

The investigator or his designee will record any additional treatments used by the subject within the 24 hours since CoolStat (e.g. NSAIDs, ice), and will also ask if they have experienced any adverse events.

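### The four 24-hour relief and freedom endpoints score only the state at the 24-hour call, which dilutes the active-sham difference on these secondary endpoints

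*Combined protocol and SAP*

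**What the plan says.** Section 9.1 tests four outcomes at 24 hours, each as a proportion in an active arm against sham. For pain they are "the proportion of subjects who show pain relief at 24 hours after active treatment" and "the proportion of subjects who show pain freedom 24 hours after active treatment". For associated symptoms they are "the proportion of subjects who show relief from migraine associated symptoms 24 hours after active treatment" and "the proportion of subjects who show freedom from migraine associated symptoms 24 hours after active treatment". The endpoint lists in sections 1.1 and 3 are built the same way, time point by time point: "Pain relief immediately post treatment and at 24 hours post treatment" and "Pain freedom immediately, 2 hours, and 24 hours post treatment". No definition asks for the same outcome at 2 hours, and none asks that the subject took nothing else in between.

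Later treatment is foreseen. Section 6.5.1 permits rescue at any point and asks only that it be put off for 2 hours where possible. Section 8.1.4 closes the clinic period with "Upon completion of these items, the subject may resume other care activities". At the 24-hour call, section 8.1.5 has staff "record any additional treatments used by the subject within the 24 hours since CoolStat". Rescue use between 2 and 24 hours is a separate secondary endpoint.

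Sections 9.3 and 9.4 contain no rule for scoring a subject who was treated before the 24-hour rating. The multiple imputation in section 9.4.2 deals with missing values only, and section 9.4.3 applies the primary methods to the secondary outcomes.

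**The concern.** Consider a subject still in moderate pain at 2 hours who takes a usual acute medication at hour 3 and reports no pain at the call. As written, this subject is a 24-hour success for relief and for freedom. So is a subject whose attack simply ran its course. So is a device responder whose pain came back and was treated.

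All of this happens in the sham arm as well, and the sham arm has more 2-hour non-responders who can convert if the device works. The 24-hour comparison then mostly asks whether the attack is over a day later. It says little about whether an early response lasted. At stake are the contrast on four secondary endpoints and the reading of the absolute 24-hour rates. A device with a durable effect could look as if its effect had faded by the next day.

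**Working it through.** **The plan's own figure.** Section 9.2 gives 17 per group for 56% v 8% at two-sided 0.05 and at least 80% power. Fisher's exact test gives power 0.774 at n = 16 and 0.813 at n = 17, so 17 reproduces. That figure concerns pain freedom at 2 hours. No 24-hour endpoint is powered in the documents.

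**Inputs.** From the documents: 25 per arm and the 2-hour rates 56% v 8% (both section 9.2). Assumed, because the documents give no 24-hour response, recurrence, resolution or rescue rate:
- a second, more modest pair of 2-hour rates, 45% v 15%;
- q = 20% of 2-hour responders lose the response, by recurrence or by taking treatment;
- r = 30%, 50% or 70% of all subjects not in sustained response are nevertheless in the favourable state at 24 hours, with r the same in every arm.

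**Formulas.** With p the 2-hour rate:
- sustained rate: S = p(1 − q)
- point-in-time rate: S + (1 − S)r
- sustained difference: (pA − pS)(1 − q)
- point-in-time difference: (pA − pS)(1 − q)(1 − r)

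The point-in-time difference is therefore the sustained difference multiplied by (1 − r). Subjects whose pain returned can recover at rate r too, which matches how the endpoint is scored.

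Power is Φ[(d − 1.96·se0)/se1], with se0 = √[2p̄(1 − p̄)/25] and se1 = √{[a(1 − a) + b(1 − b)]/25}, where a and b are the two rates, p̄ is their mean and d is their difference.

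**Worked case: 56% v 8%, r = 50%.**
- Sustained: 0.56 × 0.8 = 44.8% and 0.08 × 0.8 = 6.4%, a difference of 38.4 points.
- Point-in-time: 0.448 + 0.552 × 0.5 = 72.4% and 0.064 + 0.936 × 0.5 = 53.2%, a difference of 19.2 points.
- Power: p̄ = 0.628, se0 = 0.137, se1 = 0.134, (0.192 − 0.268)/0.134 = −0.57, giving 29%.
- Sham 24-hour responders who are not in sustained response: 0.468/0.532 = 88%.

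**All cases** (25 per arm, unadjusted two-sided 0.05):

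| 2-hour rates | Endpoint | Active v sham | Difference | Power |
|---|---|---|---|---|
| 56% v 8% | Point-in-time, r = 30% | 61.4% v 34.5% | 27 points | 48% |
| | Point-in-time, r = 50% | 72.4% v 53.2% | 19 points | 29% |
| | Point-in-time, r = 70% | 83.4% v 71.9% | 12 points | 16% |
| | Sustained | 44.8% v 6.4% | 38 points | 90% (79% at 0.05/3) |
| 45% v 15% | Point-in-time, r = 30% | 55.2% v 38.4% | 17 points | 22% |
| | Point-in-time, r = 50% | 68.0% v 56.0% | 12 points | 14% |
| | Point-in-time, r = 70% | 80.8% v 73.6% | 7 points | 9% |
| | Sustained | 36.0% v 12.0% | 24 points | 51% (34% at 0.05/3) |

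The 0.05/3 figures allow for Bonferroni over three pairwise comparisons. The powers are for a comparison of two proportions. Section 9.4 plans Kruskal-Wallis followed by Mann-Whitney tests on graded scores, so they show scale and do not reproduce the planned test.

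**The case against.** The state at 24 hours regardless of later treatment is a legitimate quantity, and the documents nowhere say that these endpoints measure durability. Rescue use is tested separately and later treatments are recorded, so a reader could set the two side by side. That stands in part. However, two separate arm-level proportions do not show which 24-hour responders had been treated.

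A reader might infer that the device is credited with successes it did not produce. The documents do not support that. Late resolution counts in every arm and the sham arm controls for it, so the harm is lost contrast and not a false benefit.

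A reader might also take it as established that the arms will converge. No 24-hour rates are given, so convergence is an inference whose size depends on r and q. If later resolution is commoner in the sham arm, for example through more rescue, the dilution is worse. If it is commoner in the active arm, the dilution is partly offset.

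A model that counts every recurrent responder as a 24-hour failure gives steeper shrinkage: at r = 50% the difference is 48 × (1 − 0.2 − 0.5) = 14.4 points, with 18% power, for 56% v 8%. That contradicts the scoring as written, under which a recurrence that was treated successfully is a success.

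Nor do the documents show that pivotal-trial planning would be damaged. The effect-size objective names no 24-hour endpoint, and the present sample size uses a 2-hour rate. Low power on a secondary endpoint breaks no stated commitment, and the sustained endpoint is itself weakly powered at 45% v 15%.

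**Conclusion.** The point holds for all four 24-hour endpoints, and nothing elsewhere in the documents repairs it. Followed as written, the plan counts natural resolution and other treatment as 24-hour response in every arm. Absolute rates rise and, if r is above zero and equal across arms, the active-sham difference shrinks by the factor (1 − r).

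Under the assumptions above, the loss is from 38 points to between 27 and 12 with the section 9.2 rates, and from 24 points to between 17 and 7 with 45% v 15%. These are illustrations. The 2-hour inputs are pain-freedom rates, the 45% v 15% pair is assumed, and so are q and r. The true size is unknown.

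The endpoints are secondary and the 2-hour primary endpoint is not affected by this point. This is a cheap improvement and not a flaw that threatens the trial's main result.

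**What to change.** In sections 3, 9.1 and 9.4.3 (and the matching list in section 1.1):
- Make the tested 24-hour pain endpoints sustained relief and sustained freedom: present at 2 hours and at 24 hours, with no rescue or additional acute treatment recorded up to 24 hours. Subjects who took such treatment count as non-responders.
- Report the point-in-time 24-hour state alongside, as a supportive result.
- For associated symptoms, apply the rule only to sustained freedom, and only among subjects who had that symptom at baseline. Section 8.1.2 rates these symptoms on a binary scale, on which relief and freedom cannot be told apart, and a subject without the symptom at baseline has nothing to be freed from.

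The change should be fixed before unblinding. It needs wording only: both ratings, the later treatments, and the date and time of rescue are already collected. No visit, procedure or rescue rule changes.

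There are two downsides. Absolute rates will be lower. A response that first appears after 2 hours counts as a failure on the sustained endpoint, although the supportive point-in-time table would still show it.

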### 6.5.1 RESCUE MEDICINE

Although the use of rescue medications is allowable at any time during the study, the use of rescue medications should be delayed, if possible, for at least 2 hours following the administration of study intervention. The date and time of rescue medication administration as well as the name and dosage regimen of the rescue medication must be recorded.

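### Rescue is permitted before 2 hours, but the rescue endpoint misses subjects whose only rescue came then, and the 2-hour pain and symptom endpoints have no rescue rule

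*Combined protocol and SAP*

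**What the plan says.** Section 6.5.1 opens its request for a 2-hour delay with the words "Although the use of rescue medications is allowable at any time during the study". Section 8.1.4 repeats the request for the clinic stay: "Subjects will be asked to delay taking rescue medications until this 2 hour period is over, if possible". Early use is therefore permitted, and the plan expects some of it, because "The study team member will record use of any rescue medications during this 2-hour period".

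The rescue endpoint in the Synopsis (1.1) and in Section 3 is "Use of rescue medication between 2 and 24 hours". Section 9.1, item 5, tests the same window, as a "Superiority comparison for use of rescue medication between 2 and 24 hours", and has no term for earlier use.

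For the primary efficacy endpoint, Section 9.1 compares proportions, each of which "is the proportion of subjects who show pain relief at 2 hours after active treatment" (or after sham). Pain freedom and symptom relief and freedom at 2 hours are defined in the same form, and none mentions rescue. Section 9.4.2 adds the rank tests on Grades 0 to 3, the Bonferroni correction and multiple imputation for missing data. Section 9.4.3 carries these methods to the secondary outcomes. Neither section says how a score obtained after rescue is treated.

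**The concern.** Two things follow if the plan is applied as written.

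- **Rescue endpoint.** A subject who takes rescue at, say, 1 hour and not again is counted with those who needed none. A subject who takes it again after 2 hours is still counted as a user.
- **2-hour endpoints.** A subject who takes rescue before the assessment and then improves is credited to the assigned arm, sham or active.

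Pain relief at 2 hours is a primary endpoint, and Section 3 makes the effect size an input to sizing a pivotal trial. A reader of that effect has to know whether it includes the benefit of rescue. If the device's own effect is wanted, more early rescue in sham shrinks it and more in active inflates it. If rescue is meant to be part of the effect, that is a defensible choice, but the plan does not state it. Left open, the choice could be made after the data are seen. The 24-hour pain and symptom endpoints have the same gap.

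**Working it through.** **Could another provision close the gap?** Multiple imputation (9.4.2) acts on missing values, and a post-rescue score is observed. The per-protocol set (9.3) requires at least 10 minutes of treatment and no major deviation. Early rescue is permitted, so it is not clearly a deviation. Nothing else in the plan addresses it.

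**Inputs from the plan (9.2, 9.4.2).** 56% versus 8% at 2 hours, two-sided alpha 0.05, 17 per group as the minimum and 25 per group planned; a Kruskal-Wallis gate, then Mann-Whitney with Bonferroni. The 17 reproduces: exact Fisher power is 77.4% at 16 per group and 81.3% at 17. The 56% and 8% are pain-freedom rates, used here as a stand-in for pain relief.

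**Assumptions (not in the documents).** Early-rescue rates of 2% to 10% per arm; at 25 per arm, 5% is 1.25 subjects and 10% is 2.5. Every early rescuer would otherwise be a non-responder. A fraction f = 0.5 (range 0.3 to 0.7) report relief after rescue.

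**2-hour endpoint.** Observed response = rescue-free response + f × early-rescue rate, so the shift in the active-minus-sham difference is f × (active rate − sham rate).

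- 2% active, 5% sham: 0.5 × (2 − 5) = −1.5 points (−0.9 to −2.1 over the range of f).
- 5% active, 10% sham: 0.5 × (5 − 10) = −2.5 points (−1.5 to −3.5).
- Reversed imbalances give +1.5 and +2.5. Equal rates give 0.

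Power was computed by exact enumeration with 25 per arm, outcome scored yes/no and both active arms at the same rate. The gate is Kruskal-Wallis at 0.05, followed by Mann-Whitney of one active arm against sham at 0.05/3.

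| Early rescue, active / sham | Observed rates (f = 0.5) | Gated power |
|---|---|---|
| 0% / 0% | 56.0 vs 8.0 | 93.8% |
| 2% / 5% | 57.0 vs 10.5 | 90.4% (88.9–91.9%) |
| 5% / 10% | 58.5 vs 13.0 | 87.1% (84.0–90.1%) |
| 5% / 2% | 58.5 vs 9.0 | 94.6% |
| 10% / 5% | 61.0 vs 10.5 | 94.6% |

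The bracketed ranges are for f from 0.7 to 0.3.

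**Rescue endpoint.** Assume any rescue by 24 hours in 60% of sham and 40% of active, a 20-point difference. Over all randomized subjects, the 2–24 hour rate = any use − early-only use.

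- Early-only 5% sham, 2% active: 55 − 38 = 17 points.
- 10% sham, 5% active: 50 − 35 = 15 points.
- 2% sham, 5% active: 58 − 35 = 23 points.
- 5% sham, 10% active: 55 − 30 = 25 points.

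No figure is offered for 24 hours.

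**The case against.** The best case for the plan is that little early rescue should occur. Subjects stay in the clinic for 2 hours and are asked to wait. The rates above have no source in the documents, and even the heavier scenario concerns about one to three subjects per arm and leaves gated power at 84% or more. Keeping observed scores whatever rescue was taken can also be a legitimate analysis. All of this stands, and it limits the size of the point. It does not supply the missing rule.

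Three stronger readings are tempting and not supported.

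- A reader might infer that all early rescue is lost from the rescue endpoint. Only early-only rescuers are lost.
- A reader might infer that early rescuers could be dropped from the denominator. Section 9.3 ties the all-randomized set to the primary endpoint, and Section 9.4.3 does not list rescue among the secondary outcomes it describes, so the denominator is not spelled out. But Section 9.1 speaks of proportions of subjects after each treatment, and nothing suggests leaving anyone out.
- A reader might infer a known bias for or against the device. The direction depends on which arm rescues early more often, and the documents do not say.

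A practical objection also stands: calling a subject a non-responder gives no value to a rank test on Grades 0 to 3, and the 2-hour assessment has a window of ±15 minutes (Section 1.3). A usable rule needs both a substituted grade and a precise cut-point.

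**Conclusion.** The point holds and should be fixed. As written, early-only rescuers count as non-users, and relief after early rescue counts as response at 2 hours. Under the stated assumptions the 2-hour difference moves by 1.5 or 2.5 points in either direction at f = 0.5. Gated power moves from 93.8% to 90.4% or 87.1%, or up to about 94.6% if the imbalance is reversed. An assumed 20-point rescue difference reads 15 to 25 points. These figures show scale only: the rescue rates, the share with relief afterwards, the yes/no scoring and the use of pain freedom for pain relief are all assumptions. The effect at 2 hours is probably small. The case for acting is that a primary endpoint, and the effect size taken from it, should have a stated meaning before the data are seen.

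**What to change.** Before unblinding:

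1. In 9.1 item 5 and the endpoint lists (1.1 and 3), count any rescue from end of treatment to 24 hours as a rescue event, over all randomized subjects. Alternatively, keep the 2–24 hour label and state that earlier use counts as use.
2. In 9.4.2 and 9.4.3, score rescue taken before the actual time of the 2-hour assessment as non-response for the pain and symptom endpoints. Where Grades 0 to 3 go into rank tests, name the substituted grade in advance, for example the baseline grade. Keep the as-observed analysis as sensitivity.
3. For 24 hours, report results both as observed and with rescue as non-response, and name beforehand which is primary.
4. Tabulate rescue by arm for 0–2 hours and 2–24 hours.

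The cost is wording and one extra table. Section 6.5.1 already requires that "The date and time of rescue medication administration as well as the name and dosage regimen of the rescue medication must be recorded". Section 8.1.4 covers the first 2 hours, and at the 24-hour call the investigator or designee "will record any additional treatments used by the subject within the 24 hours since CoolStat". The downside is that responder rates fall by f × the early-rescue rate, roughly 0.6 points (0.3 × 2%) to 7 points (0.7 × 10%) per arm over the assumed range. Nothing changes about when patients may take rescue.
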